### **2.2.3 Exploratory Endpoint**

- Effect of LB-102 on Cogstate test score

### **2.2.4 Safety Endpoints**

Safety will be assessed by the following:

- AE reporting
- Physical examination
- Vital signs
- Body weight, body mass index (BMI; derived programmatically from body weight and height measurements), and waist circumference
- Clinical laboratory tests (hematology, serum chemistry [including prolactin], urinalysis, and pregnancy tests); prothrombin time (PT), activated partial thromboplastin time (aPTT), international normalized ratio (INR), glycosylated hemoglobin (HbA1c), cortisol, adrenocorticotropic hormone (ACTH), thyroid-stimulating hormone (TSH) and total cholesterol, triglycerides, high-density lipoprotein (HDL), and low-density lipoprotein (LDL)
- 12-lead ECGs
- Assessments of EPS: the Simpson-Angus Scale (SAS), the Abnormal Involuntary Movement Scale (AIMS), the Barnes Akathisia Rating Scale (BARS)

- Columbia-Suicide Severity Rating Scale (C-SSRS)

## 2.3 Estimands

The primary study estimand is described in Table 1 below.

**Table 1.** Primary Study Estimand: PANSS Total Score at Week 4

Objective: To determine whether LB-102 [REDACTED] administered to patients with acutely exacerbated schizophrenia demonstrates antipsychotic efficacy as determined by a change from Baseline on the PANSS total score, compared to placebo	
Estimand: Treatment effect of LB-102 vs Placebo regardless of intercurrent events (treatment-policy)	
Treatment: LB-102 (50 mg or 75 mg) and matching Placebo	
ESTIMAND	ANALYSIS
Target population	Analysis set
Adult patients with acute schizophrenia as identified by the study eligibility criteria	Intent-to-Treat (ITT) analysis set, defined as all randomized patients.  Should the ITT and modified ITT (mITT) analysis sets overlap substantially (i.e. 95% of patients in the former are also in the latter), the mITT will be considered as the reference analysis set for all estimand-related analyses.
Variable	Outcome measure
PANSS Total Score at Week 4	Change from Baseline to Week 4 in the PANSS total score
Handling of intercurrent events	Handling of missing data

 
• Taking a prohibited medication prior to Week 4
 
• Starting an emergency treatment prior to Week 4
 
 
All of these intercurrent events (ICEs) will be handled via a treatment-policy strategy, i.e. data collected after their occurrence will be included in the statistical analysis of the endpoint.
	
All missing data due to study discontinuation for lack of efficacy or drug-related adverse events (AEs) will be imputed assuming a Missing Not at Random (MNAR) mechanism and assuming that after withdrawal the patients revert to the distribution of the worst PANSS score values observed up to time of discontinuation, whereas missing data due to discontinuation for any other reason, will be imputed under a Missing at Random (MAR) assumption using a Multiple Imputation (MI) approach.
 
As a sensitivity analysis, missing data that was imputed under a MAR mechanism in the primary analysis will be imputed under a MNAR mechanism using a tipping-point approach to check robustness of the main analysis

	
results. Another sensitivity analysis will adopt a reference-based imputation to further explore the impact of the MNAR assumption for missing data on the primary analysis results.
 
Another sensitivity analysis will use assessments from re-mapped early termination visits (see Section 5.2.4 for details) in the analysis, adopting the same strategy for missing data as described for the primary analysis.

Population-level summary measure	Analysis approach

In addition to the above, a secondary estimand for the secondary endpoint related to response rate (i.e. a reduction of  $\geq 20\%$  from Baseline in PANSS total score at Week 4) is also defined and presented in Table 2.

**Table 2.** Secondary Study Estimand: Response Rate (PANSS-based) at Week 4

Objective: To determine whether [REDACTED] (LB-102) administered to patients with acutely exacerbated schizophrenia demonstrates antipsychotic efficacy, as determined by a change from Baseline on the PANSS total score, compared to placebo	
Estimand: Treatment effect of LB-102 vs Placebo assuming intercurrent events classify as non-responders	
Treatment: LB-102 (50 mg or 75 mg) and matching Placebo	
ESTIMAND	ANALYSIS
Target population	Analysis set
Adult patients with acute schizophrenia as identified by the study eligibility criteria	Intent-to-Treat (ITT) analysis set, defined as all randomized patients.

	Should the ITT and mITT analysis sets overlap substantially (i.e. 95% of patients in the former are also in the latter), the mITT will be considered as the reference analysis set for all estimand-related analyses.
Variable	Outcome measure
PANSS Total Score at Week 4	Response rate, defined as a $\geq 20\%$ decrease from baseline to Week 4 in the PANSS total score
Handling of intercurrent events	Handling of missing data

 
• Taking a prohibited medication prior to Week 4
 
• Starting an emergency treatment prior to Week 4
 
 
All of these intercurrent events (ICEs) will be handled via a composite strategy, i.e. patients will be considered as non-responders
	
Missing data at Week 4 because of discontinuation due to ‘Lack of Efficacy’ or a drug-related AE will be imputed as non-responders. For all other missing data, the PANSS total score imputed for the primary analysis of the primary endpoint will be dichotomized as responders or not.
 
As a sensitivity analysis, all missing data will be imputed as non-responders.

Population-level summary measure	Analysis approach
Difference between patients treated with LB-102 (50 or 75 mg QD) and those treated with matching placebo in the PANSS response rate at Week 4 post-baseline.	
This endpoint will be analyzed using a logistic regression model including treatment and Baseline PANSS score as covariates to estimate the odds ratio (OR) of response of LB-102 (50 or 75 mg QD) vs placebo. The model will be fit separately to all imputed datasets and results pooled across imputations to obtain one single treatment effect estimate alongside 95% CI.
 
The same model will also be fit for the sensitivity analysis and a single OR (alongside its 95% CI).

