#### ***5.11.5.5 Response rate, defined as a reduction of $\geq 20\%$ from Baseline in PANSS total score at Week 4***

As described in Table 2, prior to analysis the PANSS score data imputed under a MAR mechanism will be dichotomized as being a responder or non-responder, and then missing data due to discontinuation because of lack of efficacy or drug-related AE as well as any data collected after any relevant ICE (start of emergency or prohibited treatment prior to Week 4) will be imputed as non-responders. The resulting dataset will be analyzed using a logistic regression using the response status at Week 4 as a response and baseline PANSS score, and treatment as covariates, using the below sample SAS code:

```
ods output Diffs = <output-dataset>;
proc logistic data =  descending;
  by _imputation_;
  class trt01p (ref = 'Placebo');
  model response = trt01p baseline / link = logit;
  lsmeans trt01p / diff ilink om oddsratio;
run;
```

From the above, the log odds ratio alongside its standard error will be estimated and then pooled across imputed datasets to return one single estimate, which will be exponentiated (alongside its 95% CI) to obtain an OR for each treatment arm. The proportion of responders at day 28 will also

be descriptively summarized (based purely on observed data), with an approximate 95% CI reported, derived using the following sample SAS code:

```
ods output RiskDiffCol2 = <output-dataset>;
proc freq data = ;
  table trt01p*response / riskdiff (column = 2);
run;
```

This endpoint will also be analyzed by imputing all missing data as non-responders and fitting the same logistic regression as above, from which the OR for each arm will be estimated.

Response status will be listed in the general PANSS listing.

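### SAP Table 2 defines PANSS response by a difference in response rates, but only an odds ratio is estimated, and the displayed responder proportions use observed data instead of the analysed dataset

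*SAP*

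**What the plan says.** SAP Section 2.3, Table 2, gives the population-level summary as the difference between patients on LB-102 (50 or 75 mg) and "those treated with matching placebo in the PANSS response rate at Week 4 post-baseline". Patients who take prohibited medication or start emergency treatment before Week 4 are non-responders (composite strategy). In the missing-data column, patients missing at Week 4 after discontinuing for lack of efficacy or a drug-related adverse event are also non-responders. Other missing values are dichotomized from the imputed PANSS scores.

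The analysis cell of the same row plans a logistic model "to estimate the odds ratio (OR) of response of LB-102 (50 or 75 mg QD) vs placebo". SAP Section 5.11.5.5 pools the log odds ratio, "which will be exponentiated (alongside its 95% CI) to obtain an OR for each treatment arm". The sensitivity analysis counts all missing data as non-response, "fitting the same logistic regression as above, from which the OR for each arm will be estimated".

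Section 5.11.5.5 adds that the proportion of responders at Day 28 will "be descriptively summarized (based purely on observed data), with an approximate 95% CI reported". The sample code for this is "table trt01p*response / riskdiff (column = 2").

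Protocol Section 10.4.4.3 also plans an odds ratio and states no rate difference.

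**The concern.** An estimand's summary measure should be what the analysis estimates. Here one cell names a difference in rates and the next names an odds ratio. The two are not interchangeable: turning one into the other needs the placebo rate, and the only rates the text plans to show come from a different set of patients.

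A reader of the report would see a model result in which treatment failures count as non-responders, beside proportions from which missing drop-outs have been removed. Subtracting those proportions gives something other than the Table 2 quantity. The SAP plans for 25% drop-out overall (Section 3), so the two sets of patients could differ appreciably.

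**Working it through.** **No stated figure to reproduce.** The documents give no response rate, effect or power for this endpoint. The stated power of at least 85% belongs to the primary endpoint and does not bear on this point.

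**Step 1: what each planned output delivers.**

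| Output | Measure | Data |
|---|---|---|
| Table 2 summary measure | Rate difference | Composite rule, non-responder rule, imputation |
| Main model (5.11.5.5) | Odds ratio | Follows Table 2 |
| Sensitivity model (5.11.5.5) | Odds ratio | All missing counted as non-response |
| Descriptive summary (5.11.5.5) | Proportion with CI | Observed only |

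No row pairs a rate difference with data that follow Table 2. The model code has "lsmeans trt01p / diff ilink om oddsratio", and the ILINK option does give predicted probabilities by arm. However, the ODS statement saves only the Diffs table, and the text pools only the log odds ratio. The PROC FREQ step has no BY statement for imputation.

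**Step 2: the odds ratio does not fix the difference.** For placebo rate p and odds ratio OR, the difference is OR·o/(1 + OR·o) − p, with o = p/(1 − p). With OR = 2.0 and assumed placebo rates:
- p = 10%: o = 0.111, active 18.2%, difference 8.2 points
- p = 40%: o = 0.667, active 57.1%, difference 17.1 points
- p = 60%: o = 1.5, active 75.0%, difference 15.0 points
- p = 80%: o = 4, active 88.9%, difference 8.9 points

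**Step 3: observed proportions against Table 2's rules.** Assume observed-case response r of 40% on placebo and 55% on active, a difference of 15.0 points and an odds ratio of 1.83. Let d be the share lost to lack of efficacy or drug-related adverse events. Let i be the share with prohibited or emergency medication whose Week 4 score is observed. Suppose that other missing patients, once imputed, respond at r, and that the i group would also respond at r if not recoded. The rate under Table 2 is then r × (1 − i − d).

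| d placebo / active | i placebo / active | Placebo | Active | Difference (points) | Odds ratio |
|---|---|---|---|---|---|
| 12.5% / 12.5% | 0 / 0 | 0.40 × 0.875 = 35.0% | 0.55 × 0.875 = 48.1% | 13.1 | 1.72 |
| 20% / 10% | 0 / 0 | 0.40 × 0.80 = 32.0% | 0.55 × 0.90 = 49.5% | 17.5 | 2.08 |
| 10% / 20% | 0 / 0 | 0.40 × 0.90 = 36.0% | 0.55 × 0.80 = 44.0% | 8.0 | 1.40 |
| 15% / 10% | 10% / 5% | 0.40 × 0.75 = 30.0% | 0.55 × 0.85 = 46.75% | 16.75 | 2.05 |

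The first three rows illustrate the missing-data rule alone; the last adds the composite rule. These odds ratios are unadjusted. In the third row the analysed data give an odds ratio of 1.40, while the displayed proportions, 40% and 55%, imply 1.83.

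**The case against.** The best defence is that the modelled analysis is sound. It sets post-event data and the specified drop-outs to non-response, imputes the rest, and adds an all-missing-as-non-response analysis. The odds ratio is the protocol's estimator, so one Table 2 cell may simply be loosely worded. The observed proportions are labelled descriptive. SAP Section 10 lists proportion-of-responders tables for both the main and the sensitivity analysis, and without the shells nobody can say which proportions they will show. All of this stands. It limits the weight of the point but does not make the cells agree, and the text of 5.11.5.5 specifies only observed-data proportions.

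A reader might infer more than the documents support:
- **That an observed-case rate difference is the planned one.** The text plans none. RISKDIFF appears only in sample code for the descriptive interval, on a four-arm table for which that option, meant for 2×2 tables, would need pairwise subsets.
- **That the observed proportions plainly breach the composite strategy.** In SAP Table 2 that strategy covers only prohibited and emergency medication; the drop-out rules sit in the missing-data column. The missing-data rule is departed from. The composite rule is too, unless patients with those events are recoded, which the SAP does not say. Protocol 10.4.4.3 does treat treatment-related discontinuation as a composite event for response.
- **That every drop-out is left out.** Under SAP Section 5.2.4, an early-termination assessment on Days 25 to 30 is used for Day 28 when that planned visit is missing.
- **That the odds ratio must give way as the main estimate.** Nothing in the protocol requires this.

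**Conclusion.** The mismatch is real. Table 2's rate difference is not estimated under Table 2's own rules, and the proportions shown come from a narrower dataset than the model. The observed-case difference can err in either direction: 15.0 points against 8.0 to 17.5 in the assumed scenarios. Those figures rest wholly on assumed response rates and event shares and predict nothing about this trial.

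The consequence is modest. Protocol Section 3.2 lists response as secondary (Section 10.4.4.3 calls it exploratory), and the Hochberg procedure covers only the primary endpoint. No error rate depends on this point. It should be fixed because it affects how a response rate will be read and quoted.

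**What to change.** 1. Keep the odds ratio as the protocol plans it.
2. From the same logistic model on each imputed dataset, predict every patient's response probability under each arm, average by arm to obtain standardized response rates, and take the differences from placebo for 50 and 75 mg. Obtain standard errors by the delta method and pool by Rubin's rules with a 95% CI. Do the same once for the sensitivity analysis, whose non-responder rule leaves nothing to impute.
3. Base the displayed responder proportions on that analysed dataset. If observed-case proportions are kept, label them supplementary and state whether patients with prohibited or emergency medication are recoded.
4. If the sponsor prefers the odds ratio as the only summary measure, restate the Table 2 cell accordingly; item 3 is still needed.

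SAP Section 5.11.5.1 already counts missing as non-response and reports a difference in proportions for CGI-S response, so the added display would be familiar. The cost is a few lines of SAP text and code, with no new data.

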### 3 SAMPLE SIZE

[REDACTED] patients will be randomized in a 3:3:3:1 ratio to placebo, LB-102 50 mg QD, LB-102 75 mg QD, or LB-102 100 mg QD, respectively, with [REDACTED] patients randomized to each of the first 3 arms and [REDACTED] to the last one (LB-102 100 mg). This will ensure at least 85% power at a 2-sided 5% significance level to detect a treatment difference on the primary endpoint of 8 between either LB-102 50 mg or 75 mg and placebo QD, assuming a common SD of 18, an overall drop-out rate of 25% and a Hochberg procedure to adjust for multiplicity. The sample size was estimated via Monte Carlo simulations using 10,000 simulated trials.

## 4 RANDOMIZATION

Patients will be randomized in a 3:3:3:1 ratio to placebo, LB-102 50 mg QD, LB-102 75 mg QD, or LB-102 100 mg QD. An unblinded biostatistician, contracted with [REDACTED]

[REDACTED] will be responsible for generating and implementing the randomization scheme that will determine treatment assignment. Randomization will occur through an integrated response technology (IRT) system. The IRT system will generate the randomization number and the randomization number will be captured by and integrated into the electronic data capture (EDC) system. The patient identification will be a 6-digit number (i.e., the 1-digit country number, followed by a 2-digit site number followed by a 3-digit consecutive number). Before the study is initiated, the log-in information and directions for the IRT will be provided to each site.

## 5 PLANNED ANALYSES

The Statistical Analysis Plan (SAP) and Table, Figure, Listing (TFL) Shells (and any amendments) must be approved prior to database lock (DBL). If post DBL, additional statistical analyses or changes to the statistical analysis are required, then those will be documented in a Post DBL SAP Addendum.

### 5.1 Analysis Sets

#### 5.1.1 Screened Set

The Screened Set includes all patients screened.

#### 5.1.2 Intent-to-treat (ITT) Analysis Set

The ITT Analysis Set will include all randomized patients, irrespective of whether they received the drug or not. This will be the main analysis population for efficacy analysis purposes and patients will be analyzed based on the treatment they were randomized to.

#### 5.1.3 Modified Intent-to-treat (mITT) Analysis Set

The mITT Analysis Set will include all randomized patients with at least 1 dose of study drug. This will be a secondary analysis set for the analysis of the primary endpoint, however should the ITT and the mITT substantially overlap (i.e. at least 95% of ITT patients are also in the mITT), the latter will be used as primary efficacy analysis set for all efficacy endpoints.

#### 5.1.4 Safety Analysis Set

The Safety Analysis Set will include all patients who received any study drug. Analyses based on this population will use the actual treatment received rather than the randomized one.

#### 5.1.5 Pharmacokinetic (PK) Analysis Set

The PK Analysis Set will include all patients who provide plasma concentration samples.

## 5.2 Derived Data

This section describes the derivations required for statistical analysis. Unless otherwise stated, variables derived in the source data will not be re-calculated.

### 5.2.1 Race

Where more than one race category has been selected for a patient, these race categories will be combined into a single category labelled “Multiple Race” in the summary tables. The listings will reflect the original selected categories.

### 5.2.2 Baseline

Baseline is defined as the last non-missing value (either scheduled, unscheduled, or repeat) before the patient receives the first dose of study drug.

### 5.2.3 Change from Baseline

Change from Baseline for any variable at a given visit will be calculated by subtracting the Baseline value of that variable from the value of the variable at the given visit, e.g. for the Week 4 timepoint:

$$\text{Change from Baseline to Week 4} = \text{Week 4 value} - \text{Baseline value}$$

Percent change from Baseline will be calculated as follows for all variables:

$$\text{Percent change from Baseline to Week 4} = ((\text{Week 4 value} - \text{Baseline value}) / \text{Baseline value}) \times 100$$

### 5.2.4 Early Terminations Assessments

Early termination assessments will be mapped to closest scheduled visit using the analysis windows described in Table 3. If the planned visit that an early termination assessment is mapped to has occurred and data was collected, then the early termination assessment will not be included in the statistical analyses or summaries of any endpoint but will only be included in the listing, otherwise if the planned visit hasn't occurred or it has occurred but not all applicable assessments were completed, then assessments from the early termination visit mapped to that visit will be used in the statistical analyses and summaries.

**Table 3.** Analysis Windows

Visit	Window Start Day	Window End Day
Day 8	Day 2	Day 11
Day 15	Day 12	Day 18
Day 21	Day 19	Day 24

Day 28

Day 25

Day 30

For sensitivity analyses of the primary endpoint purposes, should an early termination assessment occur that is mapped to a window where a planned visit was collected and where the PANSS score was correctly completed, the PANSS score collected at the early termination assessment will be used to replace the primary endpoint value at the planned visit.

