7.1 Schedule of Assessments

The study consists of a 7-day inpatients screening phase (up to a 7-day extension of the screening phase is allowed, if necessary with the approval of the Medical Monitor), Study Treatment Period (Days 1 to Day 28 including Baseline [Day 1]), Stabilization Period (up to 5 days, Days 29 to 33), and EoS Visit (Visit 7 [Day 42] ± 2 days). Therefore, the maximal study duration for an individual patient will be approximately up to 8 weeks.

Note, this is an inpatient study from Screening to the end of the Stabilization Period. The procedures to be performed throughout the study are outlined in the SoA (Table).

Confidential Page 53 of 102

Table do: Schedule of Assessments

Event	Screening Phase	Baseline	Study Treatment Period								End of Stabilization Period	End of Study Visit
Event	Up to 7 days ^a	Day 1	Days 2-7	Day 8 ±1	8 9-14	Day 15 ±1	Days 16-20	Day 21 ± 1	Days 22-27	Day 28 or ET	33°	Day 42± 2
Visit Number	1	2	NA ^b	3	NA ^b	4	NA ^b	5	NA ^b	6	7	8
Entrance/Screening Criteria												
Informed Consenta	X											
Admission to Inpatient Unit ^a	X											
Inclusion/Exclusion Criteria Review ^a	X	X										
Screening Adjudication Form(s) and Recordings ^d	X											
Medical History ^e	X											
MINI-Plus BPD 7.0.2	X											
Prior Medication Washout ^f	X											
Hepatitis/HIV	X											
Urine Drug and Blood Alcohol Screen ^g	X ^g											
Randomization		X										
Efficacy												
(PCRS) SCI-PANSS and CGI-S	X ^h	X ^h		X		X		X		Xh		
Cogstate Test	X^{i}	Xi								Xi		
Safety												
Prior and Concomitant Medication	X	X	X	X	X	X	X	X	X	X	X	X
Physical Exam ^j	X	X		X		X		X		X		X
AIMS	X	X^k		X^k		X^k		X^k		X^k		
SAS	X	X^k		X^k		X^k		X^k	_	X^k		
BARS	X	X^k		X^k		X^k		X^k		X^k		
C-SSRS	X ^l	X ^m		X ^m		X ^m		X ^m		X ^m	X ^m	X ^m
BMI and Waist Circumference ⁿ	X	X		X		X		X		X		

Page 54 of 102

	Screening Phase	Baseline Day 1	Study Treatment Period								End of Stabilization Period	End of Study Visit
Event	Up to 7 days ^a		Days 2-7	Day 8 ± 1	Days 9-14	Day 15 ± 1	Days 16-20	Day 21 ± 1	Days 22-27	Day 28 or ET	33°	Day 42± 2
Visit Number	1	2	NAb	3	NAb	4	NAb	5	NA ^b	6	7	8
Urine Pregnancy Test ^o	X	X								X	X	
Clinical Laboratories (for Screening and exclusionary purposes) ^p	X											
Hematology, Serum Chemistry including Prolactin, Urinalysis ^q	X	X		X		X		X		X		
TSH ^r	X									X		
PT, aPTT, and INR	X	X								X		
ACTH and Cortisol		X								X		
Resting 12-lead ECG ^s	X	X		X		X		X		X		

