8.1.1.5 Cogstate Computerized Battery of Tests

The Cogstate Computerized Schizophrenia Battery of Tests is a measure of cognitive ability in subject with Schizophrenia in both the acute and chronic stages and will take approximately 22 to 35 minutes to complete. Patients will have 1 practice session during the Screening Visit and complete the actual test on Day 1 (Baseline) and Day 28 (Visit 6) ET Visit). For each Cogstate test, the construct validity for cognitive impairment in Schizophrenia and sensitivity to change in cognition in such patients have been demonstrated in scientific literature. Patients perform the test on a provided laptop and then it is uploaded via a web-based portal.

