### 5.11.6.1 Effect of LB-102 on Cogstate test scores

Summaries for the actual and change from Baseline values for each of the Cogstate test scores (International Shopping List Test, Detection Test, Identification Test, One Back Test and Modified Groton Maze Learning Test) will be provided by treatment group. In addition, an analysis of covariance (ANCOVA) model will also be fit including pooled study site and treatment as categorical covariates and baseline Cogstate test score as continuous covariate and change from baseline to day 28 in the Cogstate test score as the response. LS means and their differences alongside 95% CIs and p-values for the comparison of active arms vs placebo will be reported. The following sample SAS code will be used:

```
ods output estimates = est LSMeans = lsm diffs = diff;
proc mixed data =  plots (only) = studentpanel(marginal);
  by test;
  class trt01pn siteid;
  model chg = trt01pn siteid base / ddfm = kr;
  lsmeans trt01pn / diff cl;
run;
```

All Cogstate test score results will also be listed.

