### 5.13.2 Laboratory Data

Descriptive statistics of the observed values and change from baseline (continuous data) will be presented by treatment group and visit for each hematology, urinalysis, chemistry, coagulation, and hormone (ACTH, TSH, cortisol) parameter. Each measurement (continuous data) will be classed as below, within, or above normal range, based on ranges supplied by the laboratory used. Shift tables in relation to the normal range from baseline to each follow-up visit will be presented.

A summary of the number of abnormal parameter values will also be provided. All laboratory data will be listed, with a separate listing only including abnormal (i.e. out of range) values.

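### SAP 5.2.4 has no early-termination rule for tests scheduled on treatment only at Day 28 or ET, so their ET values from Days 2–24 miss the Day 28 row

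*SAP*

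**What the plan says.** **Collection.** In the Schedule of Assessments (protocol 7.1), TSH is taken at Screening, the coagulation tests ("PT, aPTT, and INR") at Screening and Day 1, and ACTH and cortisol at Day 1. After that, each has an entry only in the column headed Day 28 or ET. Cogstate is the same: after a practice session at Screening, patients "complete the actual test on Day 1 (Baseline) and Day 28 (Visit 6) ET Visit" (protocol 8.1.1.5). None of these tests is planned at Day 8, 15 or 21. The ET procedures (protocol 5.3 and 7.2.14) include Cogstate and laboratory samples. Section 5.3 also asks that, where possible and reasonable, the study-completion evaluations be done when dosing stops early.

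**Mapping.** SAP 5.2.4 has one rule for all ET assessments: "Early termination assessments will be mapped to closest scheduled visit using the analysis windows described in Table 3". Table 3 has windows for Days 8, 15, 21 and 28 and none specific to a measure. If the planned visit took place and data were collected, the ET assessment "will not be included in the statistical analyses or summaries of any endpoint but will only be included in the listing". If the visit did not take place, or applicable assessments were incomplete, "then assessments from the early termination visit mapped to that visit will be used in the statistical analyses and summaries".

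**Use.** The Cogstate ANCOVA takes "change from baseline to day 28 in the Cogstate test score as the response" (SAP 5.11.6.1), and protocol 10.4.4.4 rules out imputation for it. SAP 5.13.2 summarises laboratory data by treatment group and visit, including each "coagulation, and hormone (ACTH, TSH, cortisol) parameter", with shift tables to each follow-up visit.

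**The concern.** Table 3 suits measures taken at all four on-treatment visits. For PANSS, setting an ET value aside is understandable, because a planned value of the same scale already fills that window. The five kinds of test named here have no planned value at Day 8, 15 or 21, so nothing competes with the ET value. The rule nevertheless sends it to one of those visits, where it is either excluded from summaries or placed in a row that holds only a few other early leavers.

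At stake is the visibility of a selected group. Adverse events and lack of efficacy are among the listed reasons for leaving. For TSH, coagulation, ACTH and cortisol, the ET sample is these patients' only on-treatment value. The single scheduled post-baseline row, Day 28, would describe almost only patients treated to the end or nearly so. No section of the SAP states this as a choice; it is a by-product of the window table.

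**Working it through.** **Inputs.** Table 3 windows and the two branches (SAP 5.2.4); the Day 28 or ET column (protocol 7.1); overall drop-out of 25% (SAP 3). The documents do not give the timing of drop-out or the share of ET tests completed, so both are assumptions here.

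**1. Reproduce Table 3.** Assign each study day from 2 to 30 to the nearest visit. The midpoints are (8+15)/2 = 11.5, (15+21)/2 = 18 and (21+28)/2 = 24.5. With the tie at Day 18 going to the earlier visit, the windows are 2–11, 12–18, 19–24 and 25–30. These are the stated windows; for example, the third row reads "Day 21 Day 19 Day 24".

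**2. Count the ET days before Day 28.** Days 2–27 are 26 days.

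| Mapped to | ET days | Number |
|---|---|---|
| Day 8 | 2–11 | 10 |
| Day 15 | 12–18 | 7 |
| Day 21 | 19–24 | 6 |
| Day 28 | 25–27 | 3 |

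Days mapped away from Day 28: 10 + 7 + 6 = 23, and 23/26 = 88%.

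**3. Split the 23 days by what happens to the value**, taking planned visits on their nominal days.

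| Situation | ET days | Number | Result |
|---|---|---|---|
| After a visit already held | 9–11, 16–18, 22–24 | 9 | Listing only |
| Before the visit | 2–7, 12–14, 19–20 | 11 | Stray Day 8, 15 or 21 row |
| On the visit day | 8, 15, 21 | 3 | Listing only if the planned visit counts as held |

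Listing-only is therefore 9 to 12 of 26 days (35% to 46%), and stray rows 11 of 26 (42%).

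**4. Convert to patients**, with uniform timing.
- Missing the Day 28 row, every ET test done: 0.25 × 23/26 = 0.221, about 22% of patients.
- Half the ET tests done: 0.221/2 = 0.111, about 11%.
- Listing-only, every ET test done: 0.25 × 9/26 = 0.087 to 0.25 × 12/26 = 0.115, about 9% to 12%.
- Day 28 row, per 100 patients: 75 + 25 × 3/26 = 77.9.

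**5. Vary the timing.** Share of ET values mapped away from Day 28, by weight on ET day d:

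| Timing (weight) | ET on Days 2–27 | ET on Days 2–30 |
|---|---|---|
| Uniform | 88% | 79% |
| Constant hazard (0.75^(d/28)) | 90% | 82% |
| Front-loaded, linear | 98% | 95% |
| Back-loaded, linear (d−1) | 79% | 63% |
| Back-loaded, quadratic ((d−1)²) | 70% | 50.5% |

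The range is about 50% to 98%. At 25% drop-out with every ET test done, that is 12.6 to 24.6 per 100 patients.

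**The case against.** **An early Cogstate score is not a Day 28 score.** The planned response is change to Day 28 and the protocol allows no imputation. Putting a Day 5 or Day 10 test into that model would in effect carry an early value forward. This stands: keeping such values out of the lead ANCOVA is legitimate. What is missing is a stated rule, including one that keeps ET scores out of visits where Cogstate is not given.

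**The rule can be read more kindly.** The closest scheduled visit might mean the closest visit at which that test is scheduled, which would be Day 28; but the same sentence requires the Table 3 windows, which exclude this. The two branches might instead be applied test by test, so that no TSH at Day 8 counts as no data collected there. The value would then stay in a Day 8 row and still not reach Day 28. The clause on incomplete assessments is no clear rescue either, because it concerns applicable assessments and these tests are not applicable at Days 8, 15 and 21. The ambiguity is a further reason to write the rule down.

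**Important abnormalities are captured elsewhere.** New or worsened laboratory abnormalities that are clinically significant, symptomatic, need intervention or lead to stopping the drug are recorded as adverse events (protocol 9.1.4). Out-of-range values have their own listing (SAP 5.13.2). This stands and limits the safety consequence.

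**Two stronger readings go too far.** A reader might infer that 88% of early leavers' values are dropped or appear only in listings. That figure is the share not reaching Day 28; the listing-only share is 35% to 46%. A reader might also infer that the Cogstate standard error is inflated by 13%, from √(1/0.779) = 1.133. That requires every ET test to be done and every early score to be a valid substitute for Day 28. With half the tests done the ratio is √(0.875/0.764) = 1.07. Cogstate takes 22 to 35 minutes and cannot be done within 8 hours of a benzodiazepine or sleep medication, so full completion at ET is optimistic.

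**Conclusion.** The gap is real and limited. Followed literally, SAP 5.2.4 keeps every ET value of TSH, PT/aPTT/INR, ACTH, cortisol and Cogstate from Days 2–24 out of the Day 28 row. That part follows from the text alone and needs no assumption. The split between listing-only and stray rows assumes visits on nominal days. The 88%, and the 22% of patients derived from it, assume uniform drop-out timing, and the 22% also needs every ET test to be done, so it is an upper figure for that timing.

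Only one exploratory endpoint and descriptive safety tables are affected. The documents do not support extending the point to the primary PANSS analysis or to the two dose comparisons under the Hochberg procedure: PANSS is scheduled at all four on-treatment visits and has its own ET sensitivity analysis. Nor do they support calling the Day 28 Cogstate ANCOVA wrong. The SAP should be amended because the effect is unstated, the remedy is cheap and the data are already collected.

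**What to change.** Add to SAP 5.2.4:

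- **TSH, PT/aPTT/INR, ACTH and cortisol.** The ET value is summarised in a Day 28/ET (last on-treatment) row whatever the study day, including in shift tables where these are produced. The Day-28-only row is kept beside it.
- **Cogstate.** The Day 28 ANCOVA remains the lead analysis. ET scores are not placed in Day 8, 15 or 21 rows. A Day 28/ET ANCOVA is shown as supportive only.

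The cost is a short SAP amendment before database lock, a mapping change in the programs and a few extra table rows; no new data are needed. The downside is that the Day 28/ET rows mix treatment durations from a few days to four weeks, which is why the Day-28-only results stay beside them.
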